Other safety parameters, including but not limiting to laboratory assessments and vital signs will also be summarized as appropriate.

Pharmacokinetic Analyses

Name of Sponsor/Company:	Name of Investigational Product:	Name of Active Ingredient:
Horizon Therapeutics Ireland DAC	Daxdilimab (HZN-7734)	Daxdilimab (HZN-7734)
Serum concentrations will be summarized descriptively by treatment and by visit.		
/Immunogenicity Analyses		
[REDACTED] rate of positive ADA and ADA titer will be summarized descriptively by treatment and by visit.		
Sample Size Estimate		
A sample size of approximately 210 participants (up to approximately 70 participants per treatment group) is planned for this trial. The sample size was calculated based on the primary efficacy endpoint. Assuming a placebo response rate of 25%, 70 participants per treatment group will provide approximately 80% power to detect an increase in response of 20% in a daxdilimab group as compared to the placebo group at the 2-sided alpha level of 0.10 using a Chi-square test. The minimum detectable difference is 13% between the daxdilimab group and placebo group. The assumption of 25% responder rate for placebo is based upon published results (Mejia-Vilet et al, 2021).		

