Criteria for Evaluation:

Efficacy:

Name of Sponsor/Company:	Name of Investigational Product:	Name of Active Ingredient:
Horizon Therapeutics Ireland DAC	Daxdilimab (HZN-7734)	Daxdilimab (HZN-7734)

Efficacy will be assessed by renal responses, change in proteinuria, and GFR.

Participant's experience will be assessed by the Patient Global Assessment (PtGA) and the Patient Global Impression of Change (PGI-C) scales.

Pharmacokinetics, Pharmacodynamics, and Immunogenicity

The PK of daxdilimab will be assessed by serum PK concentrations.

Daxdilimab immunogenicity will be assessed by the rate and titer of ADA.

Safety:

Safety will be assessed and will include monitoring and recording of all AEs, whether or not drug-related, measurement of vital signs, physical examinations, and monitoring of hematology, blood chemistry, and urinalysis.

Statistical Analysis on Efficacy and Safety Parameters

Efficacy Analyses

Analyses of the Primary Efficacy Endpoint:

The proportion of participants achieving CRR at Week 48 and sustained through Week 52 in the daxdilimab group will be compared to that of the placebo group using a logistic regression model with treatment, baseline eGFR value and baseline UPCR value included in the model.

Analyses of the Secondary Efficacy Endpoints:

ORR at Week 48 and sustained through Week 52 will be analyzed using a logistic regression model with treatment, baseline eGFR value and baseline UPCR value included in the model. Response in sustained reduction of OCS dose will be analyzed similarly using a logistic regression model with treatment, randomization stratification factor and baseline OCS dose included in the model.

Change from baseline in eGFR at Week 52 will be analyzed using mixed models for repeated measures (MMRM) with treatment, visit, visit by treatment interaction, randomization stratification factor (UPCR only) and baseline eGFR value included in the model.

Safety Analyses

AEs will be coded using the most recent version of Medical Dictionary for Regulatory Activities (MedDRA). The number and percentage of participants reporting TEAEs will be summarized for each treatment group by MedDRA System Organ Class and preferred terms (PT), by severity, and by relationship to the study intervention. The number and percentage of participants reporting TESAEs and TEAESIs will also be summarized.

[figure not shown]

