4. STUDY DESIGN

4.1. Overall Design

This trial is a Phase 2, multicenter, double-blind, randomized, placebo-controlled, parallel-group trial to assess the efficacy and safety of daxdilimab in patients with active, proliferative lupus nephritis despite standard of care. An overview of the trial design is presented in the schematic provided in Section 1.2 and details of trial activities are provided in Section 1.3.

Approximately 210 participants will be randomized in a ratio of 1:1:1 (70 participants per group) to receive either daxdilimab [REDACTED] mg or [REDACTED] mg SC or placebo SC in addition to SOC background therapy as described below in [Table 5](#). Randomization will be stratified by:

- Pre-randomization urine protein to creatinine ratio (UPCR) < 3.0 mg/mg vs. \geq 3.0 mg/mg
- Screening eGFR < 60 mL/min/1.73m² vs. \geq 60 mL/min/1.73m²

Table 5 First Year Treatment Assignment

Group	
1	[REDACTED]
2	[REDACTED]
3	[REDACTED]

Table 6 Second Year Treatment Assignment

Group	
1	[REDACTED]
2	[REDACTED]
3	[REDACTED]

Participants may enter the study taking daily OCS at a maximum dose of 0.5 mg/kg/day of prednisone-equivalent, not to exceed 40 mg/day, and must be on a stable dose for at least 10 days prior to Randomization. In addition, participants will receive IV methylprednisolone pulse 500 mg on the day of Randomization, prior to receiving the study intervention, unless they received a methylprednisolone pulse of \geq 500 mg within 10 days prior to Randomization followed by a reducing taper of OCS for participants already taking OCS prior to entry.

For participants who are not already taking prescribed MMF prior to Randomization, the dosing of MMF will start at 500 mg twice a day (BID) for a total daily dose of 1 gm/day for the first week, increasing to 1 gm BID for a total daily dose of 2 gm/day for the second and subsequent weeks (ie, beginning on Day 8). Prior to initiation of MMF, please refer to the restricted medications section in prior and concomitant therapy criteria because of potential interaction with MMF. An equivalent dose of mycophenolic acid (MPA) may be used as an alternative to MMF.

This trial will comprise a Screening Period of approximately 4 weeks (Days -28 to -1), a Treatment Period with Randomization on Day 1 followed by treatment through [REDACTED] ([REDACTED] totaling [REDACTED]
[REDACTED]
[REDACTED]

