4.8.1.2 Primary Efficacy Analysis

The proportion of participants achieving CRR at Week 48 and sustained through Week 52 in the daxdilimab group will be compared to that of the placebo group using a logistic regression model with treatment, adjusting for baseline eGFR value and baseline 24-hour UPCR value in the model using the full analysis set. The baseline 24-hour UPCR will be derived using the urine sample collected at Week 0 (Day 1) prior to randomization and administration of first dose of study intervention. Baseline eGFR will be based on the measurement available prior to the first dose of study intervention. The

difference in proportions of responders of daxdilimab vs placebo will be estimated together with its associated 2-sided 90% confidence interval (CI). Longitudinal presentations of results over time up to [REDACTED] based on the same analysis will be created. A bar chart will also be provided showing the proportion of participants meeting the criteria for CRR and individual components of CRR at Week 48 and maintained through Week 52 by treatment groups. A line plot over time will also be produced by treatment groups.

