4.8.1.3 Subgroup analyses of primary endpoint

The following subgroups will be investigated for the primary endpoint:

- Renal-biopsy lupus nephritis class -- the World Health Organization (WHO) or 2003 ISN/RPS classification (Class III (\pm class V) vs. class IV (\pm class V))
- Gender (male vs. female)
- Race (white, black or African American, and other)
- Ethnicity (Hispanic/Latino vs. not Hispanic/Latino)
- Baseline IFN gene signature (high vs. low)
- Age group (<65 vs. \geq 65)
- Region (North America + Western Europe vs. rest of the world)
- ADA positive at any time (yes vs. no)
- Pre-randomization urine protein to creatinine ratio (UPCR) (< 3.0 mg/mg vs. \geq 3.0 mg/mg)
- Screening estimated glomerular filtration rate (eGFR) (< 60 mL/min/1.73m² vs. \geq 60 mL/min/1.73m²)

The nominal p-value and 90% CIs of treatment effect will be provided for each subgroup analysis. Given that the number of participants in some subgroups may be limited, subgroup categories may be combined as appropriate. Otherwise, the subgroup analysis may not be performed if deemed infeasible based on sample size.

Forest plots will be generated to visually present the consistency of treatment effect in different subgroups with overall treatment effect. Other subgroup analyses may be explored as needed.

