4.8.1.5 Sensitivity Analysis

Race and ISN/RPS lupus nephritis disease class have been shown to be associated with poor prognosis and responses to treatment in patients with LN. A sensitivity analysis for

the primary endpoint with race and ISN/RPS classification included as additional covariates in the logistic regression model as defined in 4.8.1.2 will be performed to adjust the potential imbalance across treatment groups.

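### The primary CRR model could adjust for nephritis class, which the SAP itself calls prognostic; the planned test is valid, but it forgoes correction of chance class imbalance and a little power

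*Protocol*

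**What the plan says.** Protocol 1.1 and 9.4.2.1 and SAP 4.8.1.2 give the same primary model: treatment plus two baseline values. The Protocol synopsis compares the groups "using a logistic regression model with treatment, baseline eGFR value and baseline UPCR value included in the model"; the SAP has the model "adjusting for baseline eGFR value and baseline 24-hour UPCR value in the model using the full analysis set". The summary measure is the difference in responder proportions with a two-sided 90% confidence interval. The first dose is tested with this model at two-sided 0.10, and only a significant result opens the test of the second dose (Protocol 9.4.2.2, SAP 4.8.1.4).

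Randomisation is stratified by two factors only, "Pre-randomization urine protein to creatinine ratio (UPCR) < 3.0 mg/mg" against the higher range and "Screening eGFR < 60" against the higher range (Protocol 4.1, SAP 2.2).

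SAP 4.8.1.5 then states: "Race and ISN/RPS lupus nephritis disease class have been shown to be associated with poor prognosis and responses to treatment in patients with LN". It plans one sensitivity analysis with "race and ISN/RPS classification included as additional covariates in the logistic regression model", which "will be performed to adjust the potential imbalance across treatment groups". SAP 4.8.1.3 also lists class (III v IV, each with or without V) and race in three categories as subgroup factors for the primary endpoint.

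**The concern.** The SAP names two baseline factors as prognostic and mentions possible imbalance in them, but the analysis that decides the trial uses neither. Stratification does not balance them, so any difference between arms is left to chance. With 70 per arm such differences are common. If class IV participants respond less often and one arm happens to have fewer of them, the primary estimate and p-value carry that difference uncorrected. In a logistic model, leaving out a prognostic covariate also costs some power.

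The data for class are at hand: a local biopsy report of class III or IV is needed for eligibility (Protocol 5.1, criterion 6), so the local reading exists before randomisation.

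**Working it through.** **Inputs from the documents.** 70 per arm; CRR 25% on placebo and 45% on active; two-sided alpha 0.10; chi-square test (Protocol 9.2, SAP 2.3).

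**1. The plan's own figures.** The pooled rate is (0.25 + 0.45)/2 = 0.35.
- SE under the null = sqrt(2 × 0.35 × 0.65/70) = 0.0806.
- SE under the alternative = sqrt(0.25 × 0.75/70 + 0.45 × 0.55/70) = 0.0788.
- z = (0.20 − 1.645 × 0.0806)/0.0788 = 0.855, so power is 80.4%. The stated 80% reproduces.
- The smallest observed difference reaching p = 0.10 from a 25% placebo rate is 12.95 points, which matches the stated 13%.

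**2. How often class is out of balance.** Ten points of 70 is 7 participants. The class mix is not given; I take 50% and 60% class IV. The exact binomial probability that two arms differ by 7 or more is 27% at 50% class IV and 26% at 60%. (At 60%, SD = sqrt(2 × 0.6 × 0.4/70) = 0.083, and a normal approximation without continuity correction gives 23%. That is too low because the counts are discrete.)

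**3. Power with the extra covariates.** Simulation of one dose against placebo: 20,000 trials per setting, Wald test at two-sided 0.10, marginal rates held at 25% and 45%. Assumptions, none of them in the documents: 50% class IV; race mix 50/20/30; the same odds ratio (OR) for class IV v III and for the worst race level, with half that log-OR for the middle level; log-odds slope 0.4 per SD for eGFR and for UPCR.

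| Assumed OR | Planned model | Plus class and race | Change (points) |
|---|---|---|---|
| 1.0 | 82.4% | 82.1% | −0.3 |
| 0.67 | 82.2% | 82.4% | +0.3 |
| 0.50 | 81.8% | 83.1% | +1.3 |
| 0.40 | 82.3% | 84.1% | +1.8 |
| 0.33 | 82.2% | 84.9% | +2.6 |

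(Changes are taken before rounding.) Adding class alone moved power by about 0 points at OR 1.0, +0.3 at 0.67, +0.6 at 0.50 and +2 at 0.33.

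**4. False positives with no true effect.** Overall, the planned model rejects in 9.6-10.2% of trials and the model with class and race in 9.9-10.7%, against a nominal 10%.

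Now take only the trials in which active has at least 10 points fewer class IV participants. The nominal rate of wins for active is 5%.

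| Assumed OR | Planned model | Plus class and race |
|---|---|---|
| 0.67 | 6.1% | 4.3% |
| 0.50 | 8.1% | 5.8% |
| 0.33 | 9.3% | 5.8% |

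About 20,000 × 0.27/2 = 2,700 trials lie behind each rate, so the simulation SE near 5% is sqrt(0.05 × 0.95/2,700) = 0.4 points. The adjusted rates are compatible with 5%; the planned model's rates at 0.50 and 0.33 are not. The condition is on class imbalance, so the class term is what does the correcting.

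**5. Room for parameters.** Expected responders per comparison are 70 × (0.25 + 0.45) = 49, or 70 × 0.50 = 35 if both arms respond at 25%. Counting treatment and covariates, class alone makes 4 terms (49/4 ≈ 12 and 35/4 ≈ 9 responders per term). Class plus three-level race makes 6 (49/6 ≈ 8 and 35/6 ≈ 6).

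**The case against.** The strongest reply is that this is a choice of covariates, not a defect. The adjusted model is already pre-specified as a sensitivity analysis, class and race are pre-specified subgroups, and the deciding test keeps its type I error and its power. A lean primary model with wider adjustment in sensitivity is defensible. The 6-9% false-win rates hold only after conditioning on an unfavourable draw, which could be done for any omitted prognostic factor. All of this stands, and it limits the point to an improvement.

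Four stronger readings are tempting, and the documents do not support them.
- **That the SAP says adjustment is required.** It says only that a sensitivity analysis will address potential imbalance.
- **That moving covariates removes the risk of two planned p-values on opposite sides of 0.10.** Both models would still be run. In simulation they disagreed in about 3-6% of trials over odds ratios of 0.67 to 0.4, and in 2.7% with no prognostic effect at all. The primary analysis governs in any case.
- **That race should simply join class in the primary model.** The subgroup list has "Race (white, black or African American, and other" as its levels, but allows categories to be combined as appropriate without a threshold. Carried into the primary model, that freedom would let the gatekeeping test depend on the data.
- **That the same change is due for overall renal response.** SAP 4.8.1.5 concerns only the primary endpoint, and the secondary endpoints have no multiplicity control.

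What the reply does not answer is why a factor that the SAP calls prognostic, that is known before randomisation and that is not stratified, should stay out of the deciding model when including it costs almost nothing.

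**Conclusion.** The point holds as a cheap improvement. The primary test is valid: overall type I error stays near 0.10 and the 80% power claim reproduces. A reader might infer that the trial is underpowered or its primary result biased; neither follows.

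The more material loss is the correction of chance class imbalance, which reaches 10 points or more in about 26-27% of two-arm comparisons if 50-60% of participants are class IV. The power forgone is about 0 to 2 points for class alone and 0 to 3 with race, over odds ratios from 1.0 to 0.33. These gains depend on assumed prognostic effects and case mix, since the documents give neither. If class does not predict response, nothing is gained and almost nothing is lost.

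**What to change.** Before unblinding, add nephritis class (III with or without V against IV with or without V) to the primary CRR logistic model in SAP 4.8.1.2 and Protocol 9.4.2.1. State that class means the local biopsy reading that determines eligibility. This needs saying because criterion 6 accepts either the WHO or the 2003 ISN/RPS scheme, and the adjudicated reading is made only after randomisation (Protocol 8.1.4). Continue to report the difference in proportions, for example by standardising the model's predictions over the covariates.

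Keep the present two-covariate model and the race-plus-class model as sensitivity analyses. Race should enter the primary model only if its categories and any pooling rule are fixed in advance.

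The cost is a wording change in both documents, one more parameter, and a power loss of at most about 0.1 point if class is not prognostic.

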1.2. Schema

Figure 1 Trial Diagram

CRR = complete renal response; D = day; IP = investigational product; MMF = mycophenolate mofetil; MPA = mycophenolic acid; OCS = oral corticosteroids; PRR = partial renal response; [REDACTED] SC = subcutaneously; SFU = Safety Follow-Up; SOC = standard-of-care; W = week.

1.3. Schedule of Activities (SoA)

[Table 2](#) and [Table 3](#) summarize the Screening and treatment assessments and procedures for the first year of the trial and [Table 4](#) summarize the treatment and follow-up procedures and assessments for the second year of the trial.

Table 2 Screening Procedures and Assessments

Period	Screening Period
Study Day	-28 to -1
Visit Number	1
General	
Informed consent	X
Inclusion/exclusion criteria review	X
Renal biopsy ^a	See footnote ^a
EULAR/ACR SLE classification criteria	X
Demographic data	X
Medical/Surgical/SLE/LN history	X
TB assessment ^b	X
Physical examination ^c	X
Vital signs, height, and weight ^d	X
12-lead ECG (after 10 minutes rest in supine position) ^e	X
Laboratory Assessments	
███████████	█
24-hour UPCR	X
Pregnancy (serum β-hCG) test (in women of childbearing potential)	X
FSH (to confirm postmenopausal status, as appropriate) ^f	X
Serum virology ^g	X
Routine chemistry ^h	X
Hematology (CBC with differential)	X
HbA1c	X
Lipid profile ⁱ	X
Urinalysis ^j	X
███████████	█
███████████	█
███████████	█
███████████	█
███████████	█
Safety	
Concomitant medications ^k	X
AEs, SAEs, and/or AESIs	X

Table 2 Screening Procedures and Assessments

Period	Screening Period
Study Day	-28 to -1
Visit Number	1

ACR = American College of Rheumatology; AE = adverse event; AESI = AE of special interest; [REDACTED]
[REDACTED]; β hCG = β -human chorionic gonadotropin; [REDACTED] CBC = complete blood count;
[REDACTED] ECG = electrocardiogram; EULAR = European League Against Rheumatism;
FSH = follicle-stimulating hormone; HbA1c = glycosylated hemoglobin; [REDACTED]; LN = lupus
nephritis; [REDACTED] SAE = serious AE; SLE = Systemic
Lupus Erythematosus; [REDACTED]

[REDACTED] TB = tuberculosis; UPCR = urine protein to creatinine ratio; X = to be performed.

- ^a A local biopsy report indicating active, proliferative lupus nephritis will be used to confirm participant eligibility. Availability of the Screening biopsy sample (tissue, slides, or digital pathology images) for adjudication submission must also be confirmed. If a participant has not had a recent kidney biopsy within the 6 months prior to Screening, one may be performed to assess eligibility for the study provided informed consent has been given and the local biopsy report is received prior to Randomization. If a renal biopsy is performed as part of standard of care after Randomization, the results will be recorded in the electronic case report form.
- ^b The results of an IFN-gamma release assay (ie, QuantiFERON-TB Gold Plus or TSPOT) performed within 12 weeks of the Screening Visit (if available) are acceptable, provided there is no reason to suspect any re-exposure.
- ^c A complete physical examination including assessment of head, ears, eyes, nose, throat, lungs, heart, abdomen, skin, and extremities.
- ^d Vital signs include systolic and diastolic blood pressure obtained after at least 5 minutes at rest in a seated position, heart rate, respiratory rate (breaths/min), and body temperature. Height will be measured at Screening only.
- ^e Should be performed after vital signs are collected.
- ^f FSH testing does not have to be repeated if performed within 12 weeks prior to Screening (eg, re-screening).
- ^g Includes human immunodeficiency virus testing, hepatitis B testing (hepatitis B surface antigen and hepatitis core antibody [HBcAb]) Serum virology does not have to be repeated if performed within 12 weeks prior to Screening (eg, re-screening).
- ^h Refer to the Laboratory Manual for a complete list of routine laboratory assessments.
- ⁱ Participants must be fasting for at least 8 hours when lipid profiles are obtained. Visit recommended to occur in the morning.
- ^j Urine collection can be postponed for up to 14 days in women with menstrual bleeding or a urinary tract infection at the scheduled visit. Refer to the Laboratory Manual for a complete list of routine urinalysis assessments.

- ^l Use of anti-proteinuric agents (eg, ACEI/ARBs) are allowed during the study if they had been started at least 10 days prior to the assessment of the second screening 24-hour UPCR sample (ie, the first sample for 24 hour UPCR is collected at the start of the screening process and the second sample is collected within 14 days prior to the expected date of Randomization).

Table 3 First Year Treatment Procedures and Assessments

Period	Treatment Period														
Study Week															
Study Day															
Visit Window (± Days)	-	3	3	5	5	5	5	5	7	7	7	7	7	7	7
Visit Number	2	3	4	5	6	7	8	9	10	11	12	13	14	15	16
Eligibility review ^a	X														
Physical examination ^b	X				X			X			X				X
Weight	X				X			X			X				X
Vital signs ^c	X	X	X	X	X	X	X	X	X	X	X	X	X	X	X
12-lead ECG (after 10 minutes rest in supine position) ^d								X							X
Randomization ^e	X														X
	■				■			■			■				■
	■				■			■			■				■
SLICC/ACR Damage Index (SDI)	X							X							X
	■			■			■			■					■
	■			■			■			■					■
				■			■			■					■
Pregnancy (urine) test ^g	X	X	X	X	X	X	X	X	X	X	X	X	X	X	X
	■	■	■	■	■	■	■	■	■	■	■	■	■	■	■
24-hour UPCR ^h	X				X			X			X			X	X
Routine chemistry ⁱ	X	X	X	X	X	X	X	X	X	X	X	X	X	X	X
Hematology (CBC with differential)	X				X			X			X			X	X
Lipid profile ^j	X							X							X
Urinalysis ^k	X				X			X			X			X	X
	■				■			■			■			■	■
	■				■			■			■			■	■
	■				■			■			■			■	■
	■				■			■			■			■	■

Table 3 First Year Treatment Procedures and Assessments

Period	Treatment Period																					
Study Week																						
Study Day																						
Visit Window (\pm Days)	-	3	3	5	5	5	5	5	7	7	7	7	7	7	7							
Visit Number	2	3	4	5	6	7	8	9	10	11	12	13	14	15	16							
███████████	█		█		█			█			█			█	█							
███████████	█		█					█						█	█							
CCI ██████████	█		█		█			█			█			█	█							
███████████	█		█					█							█							
Daxdilimab PK (serum) ^m	X	X	X	X	X	X	X	X			X			X	X							
Daxdilimab ADA ⁿ	X		X		X			X			X			X	X							
███████████	█		█		█			█			█			█	█							
███████████	█	█						█						█	█							
███████████	█							█							█							
Screening biopsy sample shipment for adjudication ^p	X																					
███████████	█																					
Study treatment administration																						
Local injection site assessment																						
MMF/MPA/OCS dispensing ^r	X	X	X	X	X	X	X	X	X	X	X	X	X	X	X							
IV methylprednisolone administration ^s	X																					
Oral corticosteroid reduction (tapering)		X	X	X	X	X	X		X	X	X	X										
Concomitant medications ^t	◀	Continuous													▶							
AEs, SAEs, and/or AESIs ^u	◀	Continuous													▶							

ADA = antidrug antibody; AE = adverse event; AESI = AE of special interest; CBC = complete blood count; ECG = electrocardiogram; ██████████ IP = investigational product; MMF = mycophenolate mofetil; MPA = mycophenolic acid; mSFI = modified Systemic Lupus International Collaborating Clinics/American College of Rheumatology; ██████████ OCS = oral corticosteroids; ██████████ PK = pharmacokinetics;

███████████ SAE = serious AE; ██████████ X = to be performed.
 SLICC/ACR = Systemic Lupus International Collaborating Clinics/American College of Rheumatology; ██████████

^a Participant eligibility (based on Screening assessments, including non-laboratory-based assessments at Baseline [Day 1] as per the inclusion and exclusion criteria) must be checked again on Day 1 prior to Randomization.

^b Focused physical examination including assessment of head, ears, eyes, nose, throat, lungs, heart, abdomen, skin, and extremities.

- c Vital signs include systolic and diastolic blood pressure obtained after at least 5 minutes at rest in a seated position, heart rate, respiratory rate (breaths/min), and body temperature.
- d Should be performed after vital signs are collected.
[REDACTED]
- [REDACTED]
- [REDACTED]
- g Women of childbearing potential or women who are postmenopausal for less than 2 years.
- h 24-hour urine collection should begin 2 days prior to the scheduled study visit in order not to coincide with the [REDACTED] sampling due on the day of the study visit.
- i Refer to the Laboratory Manual for a complete list of routine laboratory assessments.
- j Participants must be fasting for at least 8 hours when lipid profiles are obtained. Visit recommended to occur in the morning.
- k Urine collection can be postponed for up to 14 days in women with menstrual bleeding or a urinary tract infection at the scheduled visit. Refer to the Laboratory Manual for a complete list of routine urinalysis assessments.
[REDACTED]
- [REDACTED]
- [REDACTED]
- m Blood samples will be collected in serum separator collection tubes to evaluate PK at the following visits: pre- and 6 hours (\pm 1 hour) post-injection on Day 1, prior to SC administration on [REDACTED] a single sample will be collected at the End-of-Study Visit.
- n Daxdilimab immunogenicity will be assessed by the incidence and titer of anti-drug antibodies prior to the daxdilimab administration.
[REDACTED]
- [REDACTED]
- [REDACTED]
- p The submission of the Screening biopsy sample (tissue block, slides, or digital pathology images) for adjudication should be provided within 2 months post-randomization.
[REDACTED]
- [REDACTED]
- [REDACTED]
- r For participants not on MMF or MPA during Screening, MMF/MPA therapy will start on Day 1 (Baseline – Visit 2). A quantity sufficient for a 12-week supply should be dispensed at Week 52.
- s IV methylprednisolone administered 500 mg on Day 1 (Baseline – Visit 2). If IV corticosteroids must be administered during Screening, then the [REDACTED] specimens will be collected prior to the infusion.
- t At each visit, use of any rescue therapy for worsening LN and restricted or prohibited medication beyond the protocol allowed threshold will also be assessed.
- u Participants who choose to discontinue study intervention will be contacted (either in-person at the site or through telehealth visits – video call/phone/email), if participant agrees, to assess AE/SAEs approximately 4, 8, and 12 weeks after last study intervention dose. Assessments will include of any AE/SAEs that have occurred within the last 4 weeks and will confirm if any previous AE/SAEs have resolved.

Table 4 Second Year Treatment and Follow-Up Procedures and Assessments

Period	Treatment Period												Safety Follow-up
Study Week													
In-Clinic Visit			X		X		X		X		X	X	X
Telephone or Telehealth Visit ^a	X	X		X	X		X	X		X	X		
Visit Window (± Days)	3	7	7	7	7	7	7	7	7	7	7	7	7
Visit Number	17	18	19	20	21	22	23	24	25	26	27	28	29
													30 (End-of-Study or Early Termination)
Physical examination ^b			X			X			X			X	X
Weight				X		X			X			X	X
Vital signs ^c				X		X			X			X	X
12-lead ECG (after 10 minutes rest in supine position) ^d						X						X	X
Pregnancy (urine) test ^e				X		X			X			X	X
				■		■			■			■	■
24-hour UPCR ^f				X		X			X			X	X
Routine chemistry ^g				X		X			X			X	X
Hematology (CBC with differential)				X		X			X			X	X
Lipid profile ^h						X							X
Urinalysis ⁱ				X		X			X			X	X
				■		■			■			■	■
				■		■			■			■	■
				■		■			■			■	
				■		■			■			■	
				■		■			■			■	
				■		■			■			■	
Daxdilimab PK (serum) ¹			X		X		X		X			X	X

Table 4 Second Year Treatment and Follow-Up Procedures and Assessments

Period	Treatment Period												Safety Follow-Up Period
Study Week													
In-Clinic Visit													X
Telephone or Telehealth Visit ^a	X	X		X	X		X	X		X	X		
Visit Window (± Days)	3	7	7	7	7	7	7	7	7	7	7	7	7
Visit Number	17	18	19	20	21	22	23	24	25	26	27	28	29
Daxdilimab ADA ¹			X						X				X
				■		■		■				■	■
				■				■				■	■
			■		■		■		■		■	■	■
			■		■		■		■		■	■	■
SLICC/ACR Damage Index (SDI) ^m					X							X	X
	■			■		■		■		■	■	■	■
	■			■		■		■		■	■	■	■
	■			■		■		■		■	■	■	■
		■											
Study treatment administration													
Local injection site assessment													
MMF/MPA/OCS dispensing ^q			X			X			X			X	
Oral corticosteroid reduction (discontinuation) ^r													
Concomitant medications ^s	←					Continuous			→				
AEs, SAEs, and/or AESIs ^t	←					Continuous			→				

ADA = antidrug antibody; AE = adverse event; AESI = AE of special interest; CBC = complete blood count; ECG = electrocardiogram; EOT = end-of-treatment;

IFN = interferon; IP = investigational product; MMF = mycophenolate mofetil; MPA = mycophenolic acid; [REDACTED]

[REDACTED] OCS = oral corticosteroids; [REDACTED]

PK = pharmacokinetics; [REDACTED] SAE = serious AE; [REDACTED]

[REDACTED] SLICC/ACR = Systemic Lupus International Collaborating Clinics/American College of Rheumatology; [REDACTED] X =

to be performed.

^a During the second year, participants are not required to visit the clinical site at Weeks 56, 60, 68, 72, 80, 84, 92, and 96; applicable assessments may instead be performed as a telehealth visit – video call or phone call with the participant (ie, OCS reduction, concomitant medication, and adverse event review), unless an in-person site visit is clinically indicated.

^b Focused physical examination including assessment of head, ears, eyes, nose, throat, lungs, heart, abdomen, skin, and extremities.

^c Vital signs include systolic and diastolic blood pressure obtained after at least 5 minutes at rest in a seated position, heart rate, respiratory rate (breaths/min), and body temperature.

^d Should be performed after vital signs are collected.

^e Women of childbearing potential or women who are postmenopausal for less than 2 years.

^f 24-hour urine collection should begin 2 days prior to the scheduled study visit in order not to coincide with the [REDACTED] sampling due on the day of the study visit.

^g Refer to the Laboratory Manual for a complete list of routine laboratory assessments.

^h Participants must be fasting for at least 8 hours when lipid profiles are obtained. Visit recommended to occur in the morning.

ⁱ Urine collection can be postponed for up to 14 days in women with menstrual bleeding or a urinary tract infection at the scheduled visit. Refer to the Laboratory Manual for a complete list of routine urinalysis assessments.

[REDACTED]

[REDACTED]

^k Blood samples will be collected in serum separator collection tubes to evaluate PK at the following visits: pre- and 6 hours (\pm 1 hour) post-injection on Day 1, prior to SC administration on [REDACTED]; a single sample will be collected at the End-of-Study Visit.

^l Daxdilimab immunogenicity will be assessed by the incidence and titer of anti-drug antibodies prior to the daxdilimab administration.

^m May be completed more frequently if clinically indicated.

[REDACTED]

[REDACTED]

[REDACTED]

^p Additional follow-up after Week 100 will be performed for any ongoing injection site reactions during the SFU Period.

^q A quantity sufficient for a 12-week supply should be dispensed at Weeks 64, 76, 88, and 100.

^r Continued tapering of OCS is recommended for all participants after the Week 52 Visit with the goal of achieving discontinuation (ie, 0 mg) by Week 76. Due to variability in participant responses to OCS treatment and tolerability of taper, Investigators will have flexibility of when the OCS dose is reduced at each visit.

^s At each visit, use of any rescue therapy for worsening LN and restricted or prohibited medication beyond the protocol allowed threshold will also be assessed.

^t Participants who choose to discontinue study intervention will be contacted (either in-person at the site or through telehealth visits – video call/phone/email), if participant agrees, to assess AE/SAEs approximately 4, 8, and 12 weeks after last study intervention dose. Assessments will include of any AE/SAEs that have occurred within the last 4 weeks and will confirm if any previous AE/SAEs have resolved.

